6.2.2. Dose delay and modifications for hematological toxicity

There is little experience regarding Sorafenib-induced hematological toxicity after allo-SCT. However, there may be hematological toxicity in the context of a compromised bone marrow reserve, GvHD or subsequent to viral infections, requiring dose delay and modification according to table 5.

Table 5: Hematologic Criteria for Dose Delay and Dose Modification of Sorafenib/Placebo

Toxicity Grade	Dose Delay	Dose Modification
Grade 0-2	Treat on time	No Change
Grade 3	Treat on time	DECREASE one dose level ^b
Grade 4	DELAY ^a until ≤Grade 2	DECREASE one dose level ^b

a If no recovery after 28-day delay, treatment will be discontinued unless patient is deriving clinical benefit

b If more than 2 dose reductions are required, treatment will be discontinued

6.3. Special precautions with Sorafenib

Sorafenib is approved for the treatment of renal cell carcinoma in patients after failed cytokine therapy or in those unsuitable for cytokines and for the treatment of hepatocellular carcinoma. Refer to the Summary of product characteristics (SmPC) Nexavar[®] for more detailed information.

Adverse drug reactions (ADRs) are outlined in the SmPC. If relevant new safety information is identified, the information will be integrated into an update of the SmPC which is done on a regular basis and distributed to all Investigators participating in sorafenib studies.

6.4. Other conditions during the use of Sorafenib

If the event **surgical treatment** is required, treatment with sorafenib/placebo should be discontinued 14 days prior to the planned surgery and restarted about 4 weeks after surgery.

6.5. Labeling und Handling of the medication

Packaging, labelling and distribution will be performed by the Dresden pharmacy.

The pharmacy of the University Dresden will deliver the products to the centres primary packed in wide-necked plastic bottles (120 ml PE white opaque dosed with Screw cap closure PP/PP white opaque with children proof and sealing insert) containing each 140 Sorafenib film-coated tablets 200 mg and matching placebos. 140 tablets correspond approximately to a drug supply of one month per patient. Each bottle will be pre-labelled with a tear-off label (the product identification of the packed product will be printed on the tear-off part; there will be no printing on the permanent part).

Any centre will receive from the pharmacy Dresden sufficient boxes, containing an initial drug supply of sorafenib and placebo for the first six patients. Afterwards the KKS reorders new medication in the Apotheke Dresden for the patients

The pharmacist will label the bottles according to the national regulations.

Before initiation of the study the pharmacy will be provided with a log, which already contains the package numbers and the corresponding therapy, verum or placebo. Following additional items have to be documented in the log:

- Batch number
- Expiration date of drug
- Centre, where medication was sent to
- Date of shipment

6.6. Drug accountability in the centre and diary of medication

In the centre the responsible investigator has to confirm the receipt of the study medication by fax to the pharmacy and to the KKS (needed for randomization). The fax receipt also has to be stored in the study specific file in the pharmacy. Additionally, the centre has to document the receipt of medication in a log and has to document the medication that is released to the patients in another special log, both filed in the ISF (investigator site file).

Empty boxes, medication bottles and unused study medication must be returned to the centre and documented in the drug accountability-log. The log has to be signed and stored in the ISF by the responsible investigators.

Remaining and or expired study medication and empty medication bottles have to be stored up to the monitoring visit where it is counted by the monitor and then disposed in the centres. Each disposal has to be documented and filed in the ISF.

In order to have a screening tool for the investigator each patient will receive a diary of medication that the patient has to complete.

6.7. Study medication start and discontinuation

6.7.1. Start

Patients in CHR after allo-SCT will receive sorafenib or placebo as a maintenance therapy according to the dosing schedule specified above (s. 6.2).

Treatment will start in CHR as early as possible after allo-SCT, that is, when full hematological recovery has occurred (no peripheral blasts, bone marrow blasts $\leq 5\%$, white blood cell count $> 3G/l$, platelets $>100G/l$), but earliest on day+60 and latest until day+100 after allo-SCT. Treatment will continue for two years or until relapse.

6.7.2. Discontinuation

In case of relapse the primary endpoint of this study is reached and study medication has to be stopped immediately.

Treatment of relapse will be left to the discretion of the treating investigator. Investigators should note that sorafenib should not be given after relapse.

7. Study procedures

7.1. Study evaluations

In this study it will be investigated, whether sorafenib given in the post allo-SCT setting can prevent AML relapse. To enable patient inclusion into the trial a registration screen and a base line screen is required. After a patient has passed registration and baseline screen he will be randomized and start study therapy.

A patient that fails registration or baseline screen will be considered as screening failure and will not be documented in the eCRF.

7.1.1. Registration

see section 5.4

7.1.2. Baseline screen evaluations

After a patient has been registered, the baseline screening will be performed. The baseline screen is required to ensure that a registered patient fulfils the inclusion and none of the exclusion criteria. This screen should be performed in proximity to the planned study randomization. A bone marrow aspiration must be performed no longer than 14 days before randomization in order to confirm the diagnosis of a CHR. Screening measures at baseline screen are listed below and also summarized in table 6:

- Medical and cancer history
- Physical examination
- Vital signs (heart rate, blood pressure, respiratory rate, temperature)
- Weight, height
- ECOG performance status
- Electrocardiogram
- Echocardiogram
- CBC: RBC, hematocrit, hemoglobin, WBC, differential (recorded in absolute values), reticulocytes, and platelets
- Coagulation: PT, PTT and fibrinogen
- Serum chemistry: sodium, potassium, magnesium calcium, phosphorus, chloride, renal function (BUN, creatinine), uric acid, total bilirubin, direct bilirubin, total protein, albumin, ALT, AST, alkaline phosphatase, LDH, triglycerides, amylase, cholesterol
- Urinalysis
- Pregnancy test (within 7 days before randomization)
- Thyroid profile (fT3, fT4, TSH)
- Bone marrow aspiration for cytological assessment of a CHR (within 14 days before randomization)
- Bone marrow FACS analysis
- Sampling for sorafenib resistance markers and sorafenib blood levels (20 ml heparin Blood, 10ml serum) to be sent to the laboratory of [name]. [name], Marburg
- Assessment of concomitant medications

If a registered patient fulfils the in- and exclusion criteria after the baseline screen he/she can be randomized via contacting the KKS Marburg (see 5.5).

7.1.3. Treatment evaluations (month 0 until month 24)

Patients will be seen on an outpatient basis according to the schedule outlined in table 6. This table lists all necessary assessments and indicates with an "X" when they have to be performed. All data obtained from these assessments must be supported in the patient's source documentation. Mandatory follow up visits during the treatment phase are scheduled

at 0.5, 1.5, 3, 4, 6, 8, 10, 12, 15, 18, 21, 24 and 30 months after first dosage, respectively (scheduled time point \pm 7 days during first 3 months (0,5 - 3 months) and \pm 14 days thereafter).

Treatment ends 24 months after treatment start. The following tests/evaluations have to be performed at this point:

- Physical examination
- Vital signs (heart rate, blood pressure, respiratory rate, temperature)
- Weight, height
- ECOG performance status
- CBC: RBC, hematocrit, hemoglobin, WBC, differential (recorded in absolute values), reticulocytes, and platelets
- Coagulation: PT, PTT and fibrinogen
- Serum chemistry: sodium, potassium, magnesium calcium, phosphorus, chloride, renal function (BUN, creatinine), uric acid, total bilirubin, direct bilirubin, total protein, albumin, ALT, AST, alkaline phosphatase, LDH, triglycerides, amylase, cholesterol
- Thyroid profile (fT3, fT4, TSH)
- Flt3-ITD-PCR from pB
- Sampling for sorafenib resistance markers and sorafenib blood levels (20 ml heparin Blood, 10ml serum) to be sent to the Molecular laboratory of [name]. [name], Marburg (see Appendices for laboratory submission sheet)
- Assessment of concomitant medications

7.1.4. Post study follow up evaluations (month 30 to 42)

After the treatment phase and post treatment follow up of 6 months, further follow up is planned until month 42 for evaluation of RFS and OS only (only by phone).

7.1.5. Evaluations in case of relapse

The KKS Marburg has to be informed and study medication to be stopped immediately, but un-blinding should be avoided in case of a relapse.

All evaluations that have to be performed are indicated in table 6 (M30). The following assessments are critical:

- CBC with manual blood differential and platelet counts (to be faxed to KKS)
- Bone marrow aspirate for cytological assessment of marrow infiltration and FACS analysis
- Peripheral blood molecular genetic analyses for the presence of Flt3-ITD at the MLL in Munich ([name]) or Molecular Laboratory University Dresden ([name]) (for sending see 7.2.1)
- Bone marrow and blood sampling for sorafenib resistance markers and sorafenib blood levels (20 ml heparin marrow, 20ml heparin Blood, 10ml serum) to be sent to the laboratory of [name]. [name], Marburg (see Appendices for laboratory submission sheet).

Coagulation ^e		X	X	X	X	X	X	X	X	X	X	X	X	X	X	
Serum chemistry ^f		X	X	X	X	X	X	X	X	X	X	X	X	X	X	
Urinalysis		X								X				X		
Pregnancy test ^{g, n}		X														
Thyroid profile		X					X			X				X		
Bone marrow aspiration ^h		X													X ^h	
Bone marrow biopsy ⁱ		X													X	
Flt3-ITD-PCR from pB ^a		X													X	
Bone marrow FACS analysis ^l		X													X	
Blood and bone marrow sampling ^k		X					X			X		X		X	X	
Concomitant medications		X	X	X	X	X	X	X	X	X	X	X	X	X	X	
Adverse events, continuously until end of study			X	X	X	X	X	X	X	X	X	X	X	X	X	

Months of treatment after first dosing

^a To be assessed at the “Münchener Leukämie Labor” ([name]) or “Labor für molekulare Diagnostik” of the TU-Dresden ([name]) or at another molecular laboratory approved by the sponsor
^b Vital signs include heart rate, blood pressure (sitting), respiratory rate and temperature
^c Height performed at screening only
^d CBC to include; RBC, hematocrit, hemoglobin, WBC, differential (recorded in absolute values), reticulocytes, and platelets
^e PT, PTT and fibrinogen
^f sodium, potassium, magnesium, calcium, phosphorus, chloride, renal function (BUN, creatinine), uric acid, total bilirubin, direct bilirubin, total protein, albumin, ALT, AST) and alkaline phosphatase, LDH, triglycerides, cholesterol, albumin, amylase.
^g Pregnancy test should be performed within 7 days prior to first dose of sorafenib / placebo
^h Bone marrow aspiration will be performed at baseline and in case of relapse or suspected for i) assessment of blast infiltration by cytology and by FACS and for ii) sampling purposes for later molecular studies of AML blasts in the marrow
ⁱ A bone marrow biopsy is required in the event of a dry tap or an aspiration that is inadequate for interpretation.
^j Flow cytometric analysis of bone marrow aspirations will be performed in certified laboratories experienced in flow cytometric detection of AML blasts
^k 20 ml of Heparin blood and 10ml serum will be shipped within 24 hours of collection to the laboratory of [name]. [name], Marburg (see ISF for laboratory submission sheet). 20ml of heparin bone marrow aspirat will be shipped to the same laboratory only in case a biopsy is performed, that is, at baseline and in relapse.
^l End of study is six months after last protocol treatment. This assessments indicated will also be for patients who discontinue the study for study related AE or abnormal laboratory test or diagnosis of relapse
^m follow up at month 42 for evaluation of RFS and OS only by phone.
ⁿ For Austria it is necessary to test monthly.

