5.8. Withdrawal of patients from study treatment

In accordance with the Declaration of Helsinki, each subject may voluntarily withdraw from the study at any time without giving reasons for this decision. The decision to withdraw from the study treatment must be without any prejudice for the patient.

Study treatment of a patient **may** also be terminated by the investigator for one of the following reasons:

- Severe (S)AE which make it necessary to stop study treatment
- Abnormal laboratory value(s) which make it necessary to stop study treatment
- Abnormal test procedure result(s) which make it necessary to stop study treatment
- Non-compliance with the study protocol
- Physicians decision

Study treatment **has to be** terminated for one of the following reasons:

- Subject withdrew consent
- Relapse of disease
- Pregnancy

If the investigator withdrew the patient prematurely, he has to inform the patient about his decision and has to record the primary reason for the withdrawal in the patient's medical record and on the end of treatment CRF. Safety assessments will be performed at the date of discontinuation and approximately one month after last dose of study drug. Final study evaluations will be done according to the evaluation plan outlined in table 6.

If the patient caused the premature withdrawal, all data before termination may be used for final analysis. After termination they will be followed until end of study or death. Safety assessments will be performed at the date of discontinuation and approximately one month after last dose of study drug. Off study evaluations will be done according to the evaluation plan outlined in table 6.

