11.2. Power and Sample Size Calculation

The primary endpoint of the study, relapse-free survival (RFS), is defined as the time interval from randomization until relapse or death from any cause, whichever occurs first. For a patient with none of these events before the end of study follow-up, observation of RFS will be censored at the date of his or her last follow-up examination. It is assumed that the RFS rate after 2 years may be increased from 65% with placebo (Gale et al., Blood 2005; Thiede et al., Blood 2006) to 82.5% with sorafenib, corresponding to a hazard ratio (HR) of 0.45. Comparing the sorafenib with the placebo group by a log-rank test at a two-sided alpha of 5%, 49 observed events are required to obtain a power of 80%. It is important to note that due to a decreasing likelihood of relapses over time, the Kaplan-Meier curve for RFS of Flt3-ITD AML patients after allo-SCT forms a plateau after around 2 years at the above-mentioned values.

Under these assumptions, 184 patients (i.e., 92 per group) are needed in order to observe 49 events after a minimum observation period of 24 months for each patient. The inclusion of a total of 200 patients in the study allows for compensation of a dropout rate of 8%. During the course of the study, it may be decided to adapt the number of included patients. If this is done based on a data inspection (rather than solely on the absolute number of events which occurred so far, irrespective of the study arm), the method for sample-size adaptation in survival trials developed by Schäfer and Müller (Schäfer H, Müller H-H. Modification of the sample size and the schedule of interim analyses in survival trials based on data inspections. Statist Med 2001;20:3741-3751) will be employed which ensures that the type I error risk is not affected. It may also be decided later to add one or more interim analyses using the adaptive method mentioned above, especially if the sample size is increased.

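### Table 6 ends a patient's study six months after the last dose, so scheduled RFS examinations can stop before the 24 months that section 11.2 assumes for every patient

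*Protocol*

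**What the plan says.** All references are to the protocol.

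- **Table 6, footnote l (section 7.2.1)**, attached to the column for month 30 or end of study: "End of study is six months after last protocol treatment". It continues: "This assessments indicated will also be for patients who discontinue the study for study related AE or abnormal laboratory test or diagnosis of relapse".
- **Section 5.8**, patients stopped by the investigator: safety assessments at discontinuation and about one month after the last dose, then "Final study evaluations will be done according to the evaluation plan outlined in table 6". No sentence says that follow-up continues.
- **Section 5.8**, patients who withdraw themselves: "all data before termination may be used for final analysis", and then "After termination they will be followed until end of study or death".
- **Section 7.1.3** counts the mandatory visits, through month 30, from the first dose, but describes them as belonging to the treatment phase.
- **Section 7.1.4 and Table 6, footnote m**, a later contact: "follow up at month 42 for evaluation of RFS and OS only by phone". Neither excludes early stoppers.
- **Section 11.2** sizes the trial so that 49 events are seen "after a minimum observation period of 24 months for each patient". It censors RFS at the last follow-up examination.
- **Sections 11.1 and 11.4** analyse all randomised patients by intention to treat.

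**The concern.** For a patient who completes 24 months of drug, six months after the last dose is month 30, and the two labels of the Table 6 column agree. For anyone who stops early they do not. Section 5.8 then relies on the term end of study, which only footnote l defines for an individual patient, and footnote l counts from the last dose.

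Early stops without relapse are foreseen: section 5.8 and the dose-modification tables (Tables 2 to 5) provide for them. If examinations end six months later, RFS is censored there unless the month-42 call supplies something later. Three things are at stake: events needed for the primary analysis, comparability of follow-up between arms if stopping differs by arm, and the meaning of an intention-to-treat result in which time off drug is under-observed. Sites could also read the text differently. With 45 patients randomised after 40 months (section 11.3), each event counts.

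**Working it through.** **1. The plan's own figure (section 11.2).** Two-year RFS of 65% and 82.5% gives a hazard ratio (HR) of ln(0.825)/ln(0.65) = 0.4466. Schoenfeld's formula with 1:1 allocation gives 4 × (1.960 + 0.842)² / (ln 0.4466)² = 48.3, rounded up to 49 events. The mean two-year event probability is (0.35 + 0.175)/2 = 0.2625, and 184 × 0.2625 = 48.3. Then 184/0.92 = 200. The design reproduces, and it credits every one of the 184 patients with 24 months of observation.

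**2. Where footnote l breaks that.** End of study = stop month + 6. This is below 24 for any stop before month 18, and below 30 for any stop before month 24. A stop at month 2 gives month 8; a stop at month 6 gives month 12.

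**3. Illustration of size.** The protocol gives neither stopping rates nor risk after stopping, so these are assumptions:
- 92 patients per arm; constant placebo hazard −ln(0.65)/24 = 0.01795 per month; on-drug HR 0.45, so 0.00808 per month on sorafenib.
- 30% stop early on sorafenib and 10% on placebo; the hazard after stopping equals placebo.
- With the cut, nothing is captured after stop + 6 months. This is a worst case, because it gives the month-42 call no credit.

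Hand check, using the mean stop time of 3.25 months for stops uniform over months 0.5 to 6:
- Sorafenib stoppers, 0.30 × 92 = 27.6. Event probability to month 24: 1 − exp(−(0.00808 × 3.25 + 0.01795 × 20.75)) = 0.329. To month 9.25: 1 − exp(−(0.00808 × 3.25 + 0.01795 × 6)) = 0.125. Lost: 27.6 × 0.204 = 5.6 events.
- Placebo stoppers, 0.10 × 92 = 9.2. To month 24: 0.350. To month 9.25: 1 − exp(−0.01795 × 9.25) = 0.153. Lost: 9.2 × 0.197 = 1.8 events.
- Total lost: about 7.4 of 52.6.

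Simulation of the same model (the ranges are differences between runs):

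| Stops, sorafenib / placebo | Timing (months) | HR, full 24 months | HR, cut at stop + 6 | Events, full → cut |
|---|---|---|---|---|
| 30% / 10% | 0.5–6 | 0.58–0.59 | 0.50 | 52.6 → 45.2 |
| 30% / 10% | 0–24 | 0.52–0.53 | 0.49 | about 51 → 47 |
| 20% / 5% | 0.5–6 | 0.54 | 0.48 | 51.2 → 46.5 |
| 40% / 10% | 0.5–6 | 0.63 | 0.52 | 54.1 → 44.8 |

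**4. When the HR does not move.**
- If each arm keeps its own hazard after stopping, the HR stays at about 0.45 with or without the cut, and only events are lost. For 30% / 10%, 48.3 becomes 46.3 with stops over months 0 to 24, or 44.5 with stops over months 0 to 12. Power at HR 0.45 falls from 79% to between 76% and 78%.
- If the drug has no effect and stoppers carry the placebo hazard, the HR is 1.00 with and without the cut.
- If the drug has no effect and stoppers carry 1.5 times the placebo hazard (30% / 10%, months 0.5 to 6), the HR is about 1.08 with full follow-up and 1.04 with the cut. Neither favours sorafenib.

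**The case against.** The strongest reply is that footnote l is one line under a table, and the rest of the protocol points the other way: visits are mandatory and counted from first dose, RFS and overall survival are followed to month 42, 24 months of observation is assumed for each patient, and the analysis is by intention to treat. No passage tells a site to stop RFS follow-up when drug stops, and none censors RFS at treatment stop. This stands against any claim that follow-up is definitely lost. It does not remove the conflict, because section 5.8 sends the reader to the end of study that footnote l defines.

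Three stronger readings are tempting and are not supported:
- *A reader might infer that the RFS comparison is informatively censored in favour of sorafenib.* That needs the literal reading, stopping related to relapse risk or to loss of drug effect, and no later capture of events. The documents establish none of the last three conditions.
- *A reader might infer that section 5.8 bars data collected after a patient withdraws.* Its wording is permissive, and the next sentence requires follow-up.
- *A reader might infer that the month-42 call cannot rescue RFS.* Section 7.1.4 says the call is for evaluating RFS and OS, and a relapse documented in routine care can be dated by telephone. It remains a single late contact, while section 11.2 censors at an examination.

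It is also fair that the final analysis is planned at 50 events (section 11.3), so lost events would mainly delay it.

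**Conclusion.** The passages conflict and should be reconciled. Footnote l with section 5.8 allows scheduled examinations to end six months after the last dose for patients who stop early without relapse. Section 11.2 needs 24 months for each patient, and sections 7.1.3, 7.1.4 and 11.1 imply follow-up that does not depend on treatment. This part needs no outside assumption.

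The consequence is a risk whose size depends on stopping rates, on their timing and on the hazard after stopping. With 30% against 10% stopping, the HR moves from about 0.58 to 0.59 down to 0.50, with about 7 of 53 events lost, if stops come early. It moves from about 0.53 to 0.49, with 3 to 4 events lost, if stops are spread over 24 months. What the cut removes in these scenarios is the dilution of a real effect by time off drug; it does not create an effect where there is none. Patients who stop because of relapse already have their RFS event and are not affected. Should be fixed; moderate confidence.

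**What to change.** In footnote l and section 5.8:

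- Define end of study for RFS and OS follow-up as month 30, with the month-42 contact, counted from randomisation or first dose regardless of when study drug stops.
- State that RFS and OS follow-up, including dated relapse status, continues for every randomised patient, whoever initiated the stop, unless consent to follow-up is withdrawn.
- State that neither endpoint is censored at treatment stop or at six months after it.
- Reword the sentence on data before termination to match, so that follow-up data collected afterwards are plainly included.

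The cost is amendment wording and some additional follow-up contacts for early stoppers. It is enough that dated relapse and survival status is obtained; keeping every Table 6 blood-count visit is not required for this purpose. No treatment rule changes.
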